## d. For each eye:

- Compare the final visit high contrast distance BSCVA to the high contrast distance BSCVA obtained at the Screening/Dispensing Visit. If the VA has decreased by 10 letters (0.2 logMAR) or more, explain.
- Compare the final visit keratometry readings to the Screening/Dispensing Visit keratometry readings. If there is a change of 1.00 D or more, explain.
- e. Indicate if there were any changes to pre-existing corneal scars.
- f. Collect all dispensed lenses (worn and unworn) and Study Kit(s) from the subject and return all to the Sponsor or designee using the return materials provided (refer to Section 4.5). Worn lenses will be returned in lens cases filled with Bausch + Lomb Sensitive Eyes Saline Solution.
- g. Complete the forms below and transcribe to the eCRFs.
  - Exit Visit Form

### 6.1.5 Unscheduled Visits

Additional visits may be scheduled, as necessary, to ensure the safety and well-being of subjects. All additional exams should be fully documented in the source documents and on Unscheduled Visit eCRFs, as appropriate. Visits intended to fulfill scheduled visit requirements, that fall outside the designated scheduled visit range, are not Unscheduled Visits. In these cases, the visit data will be collected and transcribed to the appropriate scheduled visit eCRF.

If a subject is seen for multiple visits during a given visit timeframe, the data from the visit that is intended to meet the protocol requirements for the scheduled visit should be captured on the visit eCRF. Where such a determination cannot be made, the first visit within the scheduled visit interval will be used for completion of the protocol required scheduled visit eCRF. Data from any additional visits within a scheduled visit interval will be captured on an Unscheduled Visit eCRF.

Subjects who require further follow-up on an AE/SAE upon discontinuation or at the conclusion of the 1-Month Follow-Up Visit will be followed according to the AE and/or Unscheduled Visit Section as necessary. At these follow-up visits, the subject should remove contact lenses s/he may be wearing. Assessments will be performed according to the investigator's judgement. The Investigator is required to follow the subject until the condition no longer warrants further follow-up for study purposes.

### NOTE: All VA measurements MUST be made using a phoropter.

- a. Determine the reason for the Unscheduled Visit.
  - If the visit is to dispense study materials only and the subject is not experiencing any problems, refer to Product Dispensing Only, Section 6.1.5.1.
  - If the subject is experiencing problems, proceed with the Unscheduled Visit assessments as needed, below.
- b. Collect the following lens wear parameters from the subject, since last visit:
  - Average number of days per week lenses were worn
  - Average number of times rewetting drops used per day on days when lenses were worn
  - Average daily wearing time
  - Average hours of comfortable wear
  - Hours lenses worn on the day of this visit
- c. Collect the Symptoms/Complaints from the subject using the 0-4 rating scales.
- d. Collect the Subjective Assessments from the subject using the 0-100 rating scales.
- e. Collect any relevant medical treatment information, including any adverse events, use of concomitant medications and/or culture that may have been taken since the last visit
- f. If the subject did not come to the visit wearing one or more study lenses, go to step g. Otherwise, evaluate the lenses (while on eye) and record the following assessments:
  - Distance lens VA
  - Over-refraction and distance VA
  - Lens wettability
  - Lens discoloration
  - Lens deposits (type, percent and degree)
  - Lens centration
  - Lens movement
  - For each eye, compare the high contrast distance lens VA to the high contrast distance lens VA obtained at the Screening/Dispensing Visit. If the VA has decreased by 10 letters (0.2 logMAR) or more, explain.
- g. Perform a slit lamp examination (remove and store the lenses in the appropriate disinfecting solution during the exam, either Biotrue multi-purpose solution, or SIMPLUS Multi-Action Solution) and record the following:
  - Any ungraded finding marked as "Present"
  - Any new corneal scars
  - Any neovascularization within the central 6 mm of the cornea

- Any corneal staining
- Any corneal infiltrate (record details on the APPENDIX C: Corneal Infiltrates Evaluation Form)
- Record and sketch any scars and slit lamp findings greater than Grade 2 in the subject's source document.
- g. If additional study rewetting drops are required at this visit, log into ORS to dispense a new Study Kit (refer to Section 4.4.2) to the subject according to ORS and InForm and record in the Product Accountability Log.
- h. If an unscheduled lens replacement is required at this visit in addition to performing assessments, dispense a new pair of subject's habitual lenses, record in Lens Accountability Log and collect the following information:
  - Primary (one) reason for replacement
  - Dispensed lens type (brand), sphere power, base curve, and diameter
- i. If Study Lenses were replaced, collect the worn lenses from the subject and place in lens case with Sensitive Eye Saline Solution and place the lens case in zippered bag with worn lens labels provided. Record in Lens Accountability Log.
- j. If the subject needs to exit the study at this visit, complete the Exit Visit as per Section 6.1.5.
- k. Complete the form(s) listed below and transcribe to the eCRF as appropriate.
  - Unscheduled Visit Form
  - Exit Visit Form (to be used if the subject is discontinued or exited at this visit)
- 6.1.5.1 Product Dispensing Only (Part of the Unscheduled Visit used only if lens and/or rewetting drop replacement is needed)

If a subject is only seen for an unscheduled lens or study drop replacement, a complete exam is not required as long as the subject is not experiencing any problems.

NOTE: For study drop replacement, an unmasked designee MUST dispense the study drops to the subject to ensure the Investigator remains masked.

- a. If study lenses and/or drops are dispensed, collect the following information in the source document and transcribe to the Product Dispensing Only eCRF Form:
  - Visit date
  - Subject ID number
  - Subject initials
  - Primary reason for replacement
- b. Record Study Kit dispensed on the Product Accountability Log. Record lenses dispensed on the Lens Accountability Log.
- 6.1.5.2 If any assessment is performed, then an Unscheduled Visit Form must be completed instead of a Product Dispensing Only Form.

### 6.1.6 Missed Visits

Missed Visits will be handled as follows:

If a subject misses the 2-Week visit and cannot be seen prior to the start of the visit range for the next scheduled follow-up visit, the visit is considered missed.

## **6.2** Study Completion

For purposes of the Investigator notifying the IRB, the study is complete when all subjects at the site have been exited. Sponsor approval is required prior to IRB notification.

### **6.2.1** Early Study Termination/Suspension

If during the study it becomes evident to the Sponsor that the study should be stopped prematurely or placed on hold, the study will be terminated, and appropriate notification will be given to the Investigator(s), IRBs, and FDA, as applicable. Bausch + Lomb will instruct the Investigators to stop/restart dispensing study materials and will arrange for study closeout, if applicable, at each site. Any subjects with ongoing Adverse Events at the time of premature study termination or hold will be followed by the Investigator, as outlined in the Safety Management Plan.

## **6.3** Concomitant Medications/Therapy

Other contact lens rewetting drops are not allowed to be used by subjects during the study.

Ocular medications or systemic or topical medications that, in the Investigator's opinion, could potentially affect ocular physiology or lens performance are also prohibited, unless medically necessary during the course of the study. Any medications that have been taken in the past 30 days before signing the ICF and any medications taken during the course of the study will be collected in the source and appropriate eCRF.

### **6.4** Treatment Compliance

The Investigator or other designee will review instructions and warnings for lens wear, lens care, handling, cleaning, disinfecting, and rewetting drop use with the subject. Any subject who does not follow instructions to a degree that, in the Sponsor or Investigator's opinion, jeopardizes the subject's well-being or the validity of the study must be discontinued.

### 6.5 Protocol Deviations

The date of and reason for deviations will be documented in all cases. Significant or major protocol deviations impacting the safety of the subject or the integrity of the study must be reported by the Investigator to the IRB immediately. Reporting of all other protocol deviations must adhere to the requirements of the governing IRB.

Subjects may continue to participate until the end of the study, unless the protocol deviations put the subject at risk or the subject's condition requires that they be discontinued from the study.

According to the Device Investigator Agreement, all investigators participating in this study agree to conduct the study in accordance with the relevant, current protocol and agree to only make changes in a protocol after being notified by the Sponsor, except when necessary to protect the safety, rights, or welfare of subjects.

Site Corrective Action plans will be developed and completed as deemed necessary by the CRO for sites or investigators who deviate from this protocol in a way that adversely affects the rights, safety or well-being of the subject(s) and/or the quality or integrity of data. The Site Corrective Action Plan will outline the deviation and the site's corrective and/or remedial actions. Decisions regarding critical deviations that merit investigator disqualification and site closure will be made by the Sponsor and documented in the Trial Master File.

#### 7.0 ADVERSE EVENTS

#### 7.1 Adverse Event Definitions

For the purposes of this study, reportable adverse events (AEs) include ocular AEs and non-ocular serious adverse events (SAEs). All AEs will be classified first for seriousness and significance and then as to whether or not they are an adverse device effect (ADE), an anticipated serious adverse device effect (ASADEs) or an unanticipated serious adverse device effect (UADEs). AEs, ADEs, ASADEs, UADEs, SAEs, Significant Non-Serious AEs and Non-Significant Non-Serious AEs are defined as follows:

### 7.1.1 Adverse Event (AE)

Any untoward medical occurrence, unintended disease or injury, or untoward clinical signs (including abnormal laboratory findings) in a subject, user, or other persons, whether or not related to the investigational medical device. This definition includes events not related to the investigational medical device, comparator, or the procedures involved. For users or other persons, this definition is restricted to events not related to investigational medical devices.

Throughout the course of this study all efforts will be made to remain alert to reportable AEs. If an AE occurs the first concern will be the safety of the subject and appropriate medical intervention will be made.

AEs should be first assessed for seriousness and significance and then differentiated for device related and non-device related.

All reportable AEs occurring after signing of informed consent and through the subject's end of participation in the study must be reported. All reportable AEs must be followed until the event resolves or stabilizes.

Applicable AEs should be photo documented and communicated to the Medical Monitor in electronic form.

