### 7.1.2 Adverse Device Effect (ADE)

An ADE is an AE that is assessed to be related to the use of an investigational medical device. This definition includes AEs resulting from insufficient or inadequate instructions for use; deployment, implantation, installation, or operation; or any malfunction of the investigational medical device. This definition also includes any event resulting from use error or from intentional misuse of the investigational medical device.

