### 7.1.2.1 Anticipated Serious Adverse Device Effect (ASADE)

An ASADE is an ADE that first meets the serious criteria (see Section 7.1.3) or significant non-serious criteria (see Section 7.1.4) and which, by its nature, incidence,

severity or outcome, has been previously identified in the investigational plan or application (including a supplementary plan or application) and/or in the risk analysis report. ASADEs include:

- Corneal Ulcer (infectious or non-infectious)
- Keratitis
- Sensitivity to light (photophobia)
- Excessive eye secretions including mucopurulent discharge
- Blurred vision, rainbows or halos around objects
- Poor visual acuity (reduced sharpness of vision)
- Moderate to severe eye pain not relieved by removing the lens

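### Section 7.1.1 leaves device-related harm to users and other persons who are not trial subjects outside the AE definition (wording error, low severity)

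*Combined protocol and SAP*

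**What the plan says.** The first paragraph of Section 7.1.1 opens broadly. It counts as an AE any untoward occurrence "in a subject, user, or other persons, whether or not related to the investigational medical device". It closes with a limit on two of those three classes: "For users or other persons, this definition is restricted to events not related to investigational medical devices".

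The later definitions are nested inside this one:

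- Section 7.1.2: "An ADE is an AE that is assessed to be related to the use of an investigational medical device". The same section adds: "This definition also includes any event resulting from use error or from intentional misuse of the investigational medical device".
- Section 7.1.2.1: "An ASADE is an ADE that first meets the serious criteria" (or the significant non-serious criteria).
- Section 7.1.2.2 likewise makes a UADE a kind of ADE.
- Sections 7.1.3 and 7.1.4 define the SAE and the significant non-serious AE as AEs that meet further conditions.

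Section 7.1.1 also gives the order of assessment: "AEs should be first assessed for seriousness and significance and then differentiated for device related and non-device related".

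**The concern.** A safety definition that extends beyond subjects would be expected to pick up harm that the product may have caused. For users and other persons this one does the reverse. It keeps events that say nothing about the drops and leaves out those that might. The ADE, ASADE and UADE classes all start from the AE, so the omission carries through the chain. Section 7.4 attaches its duties to these classes: 24 hours to the Medical Monitor for SAEs and significant non-serious AEs, and at most 10 working days to the IRB for UADEs. An event outside the classes does not start either clock by virtue of the AE definitions.

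Contact by non-subjects is foreseeable. The drops are kept at home for about a month, and the subject instructions (Appendices E and F) warn that they be kept away from children. Unmasked designees handle kits and returned, opened containers (Sections 4.5 to 4.7).

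**Working it through.** The plan gives no figure on this point and no arithmetic applies. The check follows the definitions in order.

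**Step 1. The AE set.** For subjects, the opening of 7.1.1 applies without a limit, so related and unrelated events are both AEs. For users and other persons, the closing sentence leaves only unrelated events.

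**Step 2. The ADE set.** By 7.1.2, ADE = AE and related. For subjects this is the related part of their AEs. For users and other persons it is the overlap of unrelated and related events, which is empty.

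**Step 3. The classes above.** ASADE and UADE are kinds of ADE, so they too are empty for users and other persons. An SAE is an AE that meets the serious criteria, so a serious device-related injury to a non-subject is not an SAE either.

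| Person and event | AE (7.1.1) | Can be ADE, ASADE or UADE |
|---|---|---|
| Subject, related | yes | yes |
| Subject, unrelated | yes | no |
| User or other person, unrelated | yes | no |
| User or other person, related | no | no |

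The last row is the fault.

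**Step 4. Other routes that might catch the last row.**

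- *Use-error and misuse clause (7.1.2).* It speaks of any event and is not limited to subjects, so it may bring some cases back. It sits under a definition that requires an AE first, and it does not reach harm from correct use or incidental exposure.
- *UADE catch-all (7.1.2.2).* Its final clause concerns the rights, safety or welfare of subjects, so it does not help non-subjects.
- *Device deficiencies (7.4.2).* Malfunctions, use errors and labeling faults go to the Medical Monitor within 24 hours and then to the Sponsor, who must document whether they could have led to an SAE. This route records the fault, not the injury, and an injury without a deficiency does not enter it.
- *Relationship scale (7.3.2).* It grades whether an AE is related, so it presupposes an AE.
- *Safety Management Plan.* Section 7.4 refers to it for the full reporting process. It is not among the documents reviewed, so its content is unknown.

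The part that no visible route covers is device-related harm to a non-subject that arises without use error, misuse or a device deficiency.

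**The case against.** The other side concedes that the word *not* is probably a slip, and argues that little follows from it.

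- *Subjects are not affected.* A reader might infer that, because subjects instil the drops themselves, they are users and fall under the restriction. The text does not support this. Section 7.1.1 names subjects, users and other persons separately and covers subjects "whether or not related to the investigational medical device". This objection stands in full.
- *The reporting chain is not wholly closed.* A reader might also infer that device-related harm to a non-subject could never reach the Medical Monitor, Sponsor or IRB. That goes too far, given the use-error clause, the device deficiency route and the unseen Safety Management Plan. This stands as a limit on the claim; it does not fill the gap left in the last step of the check.
- *The group is small.* The drops are self-administered, the designee only instructs and watches at dispensing, and the Safety Population (8.5.3) contains dispensed subjects only. This stands, and it is why severity is low.
- *A restriction always narrows the general rule before it, so the paragraph need not contradict itself.* This is fair as far as it goes. The real fault is the direction of the restriction, which leaves 7.1.2 nothing to act on for these persons.
- *Deleting one word may not be enough.* The duty to report is framed around a subject: "All reportable AEs occurring after signing of informed consent and through the subject's end of participation in the study must be reported". A non-subject neither consents nor ends participation. This stands as a reason to check the reporting instructions when the sentence is corrected. It does not justify leaving the sentence as it is.

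**Conclusion.** The definition is wrong as written, with low severity. For users and other persons who are not subjects, the AE-based definitions include unrelated events and exclude device-related ones. AE, ADE, ASADE and UADE capture for trial subjects is intact.

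The documents do not state how many events could be affected. The number is probably small, and some of those events may surface by other routes. No primary endpoint, hypothesis, planned analysis or sample size depends on the sentence.

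The conclusion rests on a literal reading of Sections 7.1.1 to 7.1.3. It assumes that the AE form and the Safety Management Plan do not already override the wording. That *not* is a drafting slip is an inference from the sense of the text; the finding does not depend on it.

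**What to change.** Reconcile Section 7.1.1 with Section 7.1.2 so that device-related events in users and other persons are AEs. The simplest change is to delete *not* from the closing sentence of the first paragraph of 7.1.1, so that the limit for these persons keeps related events. Deleting the whole sentence would also remove the conflict, but would leave unrelated events in non-subjects within the definition.

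At the same time, check that the AE form and the Safety Management Plan do not repeat the wording, and that they make clear how and when an event in a non-subject is reported.

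The edit is one word, but Section 3.5 requires IRB approval of an amendment and site training before it is implemented. The cost is therefore a minor amendment with site notification, and it could be carried with the next amendment. Nothing in the statistical sections needs to change.

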### 7.1.2 Adverse Device Effect (ADE)

An ADE is an AE that is assessed to be related to the use of an investigational medical device. This definition includes AEs resulting from insufficient or inadequate instructions for use; deployment, implantation, installation, or operation; or any malfunction of the investigational medical device. This definition also includes any event resulting from use error or from intentional misuse of the investigational medical device.

### 7.1.2.1 Anticipated Serious Adverse Device Effect (ASADE)

An ASADE is an ADE that first meets the serious criteria (see Section 7.1.3) or significant non-serious criteria (see Section 7.1.4) and which, by its nature, incidence,

severity or outcome, has been previously identified in the investigational plan or application (including a supplementary plan or application) and/or in the risk analysis report. ASADEs include:

- Corneal Ulcer (infectious or non-infectious)
- Keratitis
- Sensitivity to light (photophobia)
- Excessive eye secretions including mucopurulent discharge
- Blurred vision, rainbows or halos around objects
- Poor visual acuity (reduced sharpness of vision)
- Moderate to severe eye pain not relieved by removing the lens

### 7.1.2.2 Unanticipated Serious Adverse Device Effect (UADE)

An UADE is an ADE that first meets the serious criteria (see Section 7.1.3) and has an effect on health or safety or any life-threatening problem or death caused by, or associated with, a device if that effect, problem or death was not previously identified in nature, severity or degree of incidence in the investigational plan or application (including a supplementary plan or application), or any other unanticipated serious problem associated with a device that relates to the rights, safety, or welfare of subjects.

### 7.1.3 Serious Adverse Event (SAE)

An AE that:

- Led to death;
- o Led to serious deterioration in the health of the subject, that resulted in:
  - A life-threatening illness or injury; or
  - A permanent impairment of a body structure or a body function (e.g., blindness); or
  - Inpatient or prolonged hospitalization; or
  - Medical or surgical intervention to prevent life-threatening illness or injury or permanent impairment to a body structure or a body function;
- Led to fetal distress, fetal death, or a congenital abnormality or birth defect.

Note: A planned hospitalization for a pre-existing condition, or a procedure required by the protocol, without serious deterioration in health, is not considered an SAE.

Serious adverse events are also those events that result in, or have potential to cause, either permanent impairment of an ocular function or damage to an ocular structure and may necessitate medical or surgical intervention.

Serious adverse events may include any hazardous, sight-threatening conditions occurring after exposure to the test article, including the following:

- A presumed infectious ulcer (defined as a progressive erosion of the corneal tissue). For the purposes of reporting, this includes:
  - Central or para-central location;
  - o Penetration of Bowman's membrane;
  - o Infiltrate  $\geq 2$  mm diameter;

- Associated with iritis;
- o Associated with any increase in intraocular pressure;
- o Culture positive for microorganisms;
- o Increasing size or severity at subsequent visits;

NOTE: Signs of a presumed infectious corneal ulcer may include irregular focal infiltrates, active lesions with raised edges, significant diffuse infiltration, anterior corneal to mid-stromal involvement, erosion with overlying staining, conjunctival and lid edema, anterior chamber reaction (iritis), and severe bulbar and limbal redness. Symptoms associated with a presumed infectious ulcer (microbial keratitis) may include pain of rapid onset, severe redness, purulent or mucopurulent discharge, tearing, and photophobia.

- Any central or paracentral (within 6 mm of cornea) corneal event that results in permanent opacification (such as corneal scar or vascularization);
- Any serious adverse ophthalmic events including hypopyon and/or hyphema;
- Any neovascularization within the central 6 mm of the cornea;
- Permanent loss of >2 lines of BSCVA:
- All cases of iritis.

